11.1 AML

For the AML patients, the historical data suggested the overall response rate to current standard treatment is 25%. The target response rate is 40%. The trial will be continuously monitored. The study will be stopped early if the data suggest that:

$$\Pr(\pi > 0.25 | \text{data}) < 0.3$$

Here π is the overall response (OR) rate. That is, if at any time during the study we determine that there is a less than 30% chance that the average OR rate is greater than 25%, we will terminate the study. The OR rate is assumed to follow a non-informative prior of Beta (0.5, 1.5). The study will be stopped early if (The number of overall responses)/ (The number of patients evaluated) $\leq 1/8, 2/11, 3/15, 4/20, 5/24, 6/29, 7/33, 8/37, 9/42, 10/46, 11/50, 12/54, 13/59$.

Table 2: Operating characteristics for monitoring of overall response rate in AML patients

True Response Rate	Early Stopping Probability	Median Sample size (interquartile)
0.2	0.91	8 (8,20)
0.25	0.73	11 (8, 60)
0.3	0.51	54 (8, 60)
0.35	0.33	60 (15, 60)
0.4	0.19	60 (60, 60)

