1. OBJECTIVES

Phase I

Primary:

To determine the maximal tolerated dose (MTD) of clofarabine to be used in portion II of the study

Phase II

Primary:

To determine the response rate of the DAC-CIA regimen

Secondary:

- A) To determine the toxicity of the combination regimen
- B) To determine the disease-free survival (DFS) and overall survival (OS) rates

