2. RATIONALE

2.1 Acute Myelogenous Leukemia

Acute myelogenous leukemia (AML) is the most common acute leukemia in adults. It is estimated that 13,780 men and women will be diagnosed with and 10,200 men and women will die of acute myeloid leukemia in the year 2012.¹ AML is a disease with a poor prognosis with a 5-year survival of only around 30%.^{2,3} Certain subgroups of AML have a particularly worse

outcome such as patients with relapsed and/or refractory AML and AML arising from antecedent myelodysplastic syndrome (MDS) or myeloproliferative neoplasms (MPNs).

Although most patients with AML will achieve remission with induction chemotherapy; many patients will relapse, despite the administration of post-remission therapies. Relapses may occur weeks to many years later. Up to 10% of patients will be refractory to induction chemotherapy. Both of these groups of patients (relapsed/refractory) constitute a particularly poor risk group. Although an allogeneic stem cell transplant would be considered a recommended approach for most of these patients, it is feasible only in a small number of patients. Many novel drugs and approaches are being investigated for this group of patients. However, the CR rates have been, in general, less than 30%.⁴⁻⁶ The Eastern Cooperative Oncology Group (ECOG) conducted a randomized 3-arm phase II trial where relapsed/refractory AML patients received either intermediate-dose cytarabine/gemtuzumab ozogamicin, or intermediate-dose cytarabine/liposomal daunorubicin, or intermediate-dose cytarabine/ cyclophosphamide/ topotecan.⁴ The CR/CRp (CR with incomplete platelet count recovery) rates achieved were low, ranging from 4% to 12%, depending on the study arm. Cortes et al. performed an exploratory study in relapsed/refractory AML patients combining p53 antisense oligonucleotide Cenersen with idarubicin either alone or with cytarabine.⁵ Ten of the 53 (19%) patients achieved CR/CRp. These data highlight the need for development of better treatment strategies for this group of patients.

AML arising from antecedent MDS/MPN: In a recent study by Bello and colleagues, outcomes of patients who progressed from MDS were studied.⁷ In the subgroup of patients who had failed hypomethylating agents (the current FDA approved standard therapy for MDS), the median overall survival (OS) was only 3.7 months from the time of AML diagnosis. Those with poor

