2.3 Clofarabine in AML

Clofarabine (2-chloro-20-fluoro-deoxy-9-b-D-arabinofuranosyladenosine) is a second-generation nucleoside analog, which was developed as a hybrid molecule to combine the most favorable pharmacokinetic properties of both fludarabine and cladribine and has better stability with higher affinity to deoxycytidine kinase, the rate-limiting step in phosphorylation of nucleosides.¹²

Clofarabine acts as an inhibitor of both DNA synthesis and the enzyme ribonucleotide reductase (RNR). Its structural characteristics render it resistant to deamination by adenosine deaminase and phosphorolytic cleavage by bacterial purine nucleoside phosphorylase.¹³⁻¹⁶ Single agent clofarabine has demonstrated activity in phase I-II studies in AML.^{17,18} As a potent inhibitor of ribonucleotide reductase (RNR) and by means of biochemical modulation, clofarabine is more ideally suited to be incorporated into combinations such as have been tested and validated with cytarabine in AML.¹⁹ We have previously conducted a study combining cytarabine with clofarabine in patients with relapsed/refractory AML.²⁰ At doses of 1 g/m2 daily x 5 days for cytarabine and 40 mg/m2 daily x 5 days for clofarabine, we reported a response rate of 40% (28% complete remission) in 29 patients with a median age of 59 years (18 to 84 years).

Responses extended to patients with primary refractory disease and those with abnormal cytogenetics. Other groups have since followed this lead and published comparable results.²¹ We have also reported adaptively randomized study of lower-dose clofarabine (30mg/m2 IV daily for 5 days) with or without low-dose cytarabine (20mg/m2 SQ daily for 14 days) in previously untreated older (≥ 60 years) with AML. CR rate was significantly higher with the combination therapy (63% vs. 31%; $p=0.025$). The combination arm also had improved event free survival (7.1 months vs. 1.7 months; $p=0.04$), but not overall survival (11.4 months vs. 5.8 months; $p=0.1$). No excess toxicity was observed in the combination arm. We have previously explored

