the combination of clofarabine with cytarabine and anthracycline (CIA regimen). In a phase I study for patients with relapsed/refractory AML, the following doses were established for further evaluation: clofarabine 22.5 mg/m² daily x 5 days, idarubicin 6 mg/m² daily x 3 days, and cytarabine 0.75 mg/m² daily x 5 days.²² In a recent update of a phase II study of 63 patients treated with CIA regimen,²³ the overall response rate was 38% including 21% CR. Median overall survival was 34 weeks for all patients and 66 weeks for those patients who achieved CR/CRp. Twenty-four patients (38%) were able to proceed with a stem cell transplant. Induction mortality was at 8%. Toxicities were manageable.

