Based on these observations, we hypothesize that addition of decitabine to our current standard chemotherapy regimen (clofarabine, idarubicin, cytarabine), the DAC-CIA regimen, would be synergistic and would ultimately lead to an improvement in CR rates and patient outcomes. We propose a phase I-II study. The primary endpoint of the phase I study is to determine the maximal tolerated dose (MTD) of clofarabine to be used in the phase II portion of the study. The primary endpoint of the phase II study is to determine the response rate of DAC-CIA regimen.

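### Does the 25% AML benchmark in section 11.1 need to change because the protocol reports 38% for the CIA backbone?

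*Combined protocol and SAP*

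**What the plan says.** Section 11.1 gives the AML reference and target: "the historical data suggested the overall response rate to current standard treatment is 25%. The target response rate is 40" per cent. No source or population is attached to the 25%. The rule stops the AML cohort if Pr(π > 0.25 | data) falls below 0.3, under a Beta(0.5, 1.5) prior and with at most 60 patients.

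Section 2.3 reports the earlier CIA phase II series of 63 patients: "the overall response rate was 38% including 21% CR". Section 2.5 then hypothesizes that "addition of decitabine to our current standard chemotherapy regimen (clofarabine, idarubicin, cytarabine), the DAC-CIA regimen, would be synergistic". On outcomes, the same sentence expects that the combination "would ultimately lead to an improvement in CR rates and patient outcomes".

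The formal phase II objective in section 1 is narrower: "To determine the response rate of the DAC-CIA regimen". Section 11 describes phase II as single arm. Its Analysis method paragraph plans a posterior mean and a 90% credible interval for overall response, and nothing further for efficacy.

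Other rates for relapsed or refractory AML also appear. In section 2.1, CR/CRp in a three-arm trial is described as "rates achieved were low, ranging from 4% to 12%, depending on the study arm", and for a second study "Ten of the 53 (19%) patients achieved CR/CRp". The same section puts CR rates with novel approaches at generally under 30%. For clofarabine plus cytarabine, section 2.3 says "we reported a response rate of 40% (28% complete remission) in 29 patients".

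**The concern.** The idea of a current standard appears in two places with two different rates. In section 2.5 it is CIA, for which section 2.3 gives 38%. In section 11.1 it is a treatment with a 25% response rate. If both mean CIA, the benchmark is 13 points too low and the 40% target is only 2 points above what the backbone already achieved.

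The stake is interpretation of the main AML result. Read against 25%, a result on target looks decisive. Read against 38%, it says little about whether decitabine adds anything, which is the hypothesis that motivates the trial. A regimen no better than its backbone could finish accrual and be reported as support for the addition.

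**Working it through.** **Inputs.** Section 11.1: prior Beta(0.5, 1.5), reference 0.25, stopping list 1/8, 2/11, …, 13/59, maximum 60 patients, Table 2. Section 2.3: 38% of 63 patients, which implies 0.38 × 63 ≈ 24 responders.

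**1. The plan's own figures.** An exact binomial recursion over the printed list, with the first stop possible at 8 patients, gives these early stopping probabilities:

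| True rate | Table 2 | Recomputed |
|---|---|---|
| 0.20 | 0.91 | 0.906 |
| 0.25 | 0.73 | 0.725 |
| 0.30 | 0.51 | 0.504 |
| 0.35 | 0.33 | 0.318 |
| 0.40 | 0.19 | 0.187 |

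The design does what it says. Only the choice of reference is in question.

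**2. If decitabine adds nothing.** The backbone rate in this population is not given, so a range is assumed. The last two columns are illustrative readings and not plan criteria: 21/60 is the smallest count whose 90% credible interval lies above 0.25, and 24/60 is the target rate.

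| Assumed backbone rate | Completes 60 | Completes with ≥21 | Completes with ≥24 |
|---|---|---|---|
| 0.25 | 28% | 4% | 0.7% |
| 0.30 | 50% | 19% | 6% |
| 0.35 | 68% | 45% | 22% |
| 0.38 | 77% | 62% | 38% |

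The concern has force only if the backbone rate is well above 0.25.

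**3. A result on target.** After 24/60 the posterior is Beta(0.5 + 24, 1.5 + 36) = Beta(24.5, 37.5). Its mean is 24.5/62 = 0.395 and its 90% credible interval is 0.296 to 0.498. From it, Pr(π > 0.25) = 0.99 and Pr(π > 0.38) = 0.59.

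**4. Would extra threshold probabilities add information?** Pr(π > 0.38) > 0.95 is the same statement as the lower 90% limit lying above 0.38.

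| Responders | 90% credible interval | Pr(π > 0.38) |
|---|---|---|
| 29/60 | 0.373 to 0.580 | 0.936 |
| 30/60 | 0.388 to 0.596 | 0.963 |

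Both cross at 30/60. The planned interval already carries the information.

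**5. Is 38% the right reference?** Taking 24/63, the exact 95% confidence interval is 26% to 51%, so the figure is imprecise. It is also not like for like:
- The doses established for CIA in section 2.3 differ from those in section 5.2.1 (clofarabine 22.5 against 15 mg/m², idarubicin 6 against 10 mg/m²).
- Section 4 also admits AML arising from MDS or MPN that has not been treated as AML, a group for which section 2.1 gives a CR rate under 20%.
- Section 2.3 does not say what its overall response comprises or over what period. Section 11 counts CR, CRp or CRi within 56 days.

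**6. Is 25% defensible?** It lies inside the span of the protocol's own figures, from 4–12% and 19% up to 40%, and agrees with the general statement of CR rates under 30%. That statement concerns CR and not the wider endpoint, so it supports 25% without fully sourcing it.

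**The case for a change.** The strongest case for a change is that the hypothesis in section 2.5 leads directly to the phase II endpoint, so readers will judge the result by it. A cohort at exactly 40% gives 0.99 against the only reference the plan names and 0.59 against the reported rate of the regimen to which decitabine is added. If the CIA rate is treated as uncertain (24/63, same prior) and exchangeable with this trial, the probability that the four-drug rate exceeds it is 0.58. Stating in advance that the trial speaks to activity and not to an added effect, and reporting a few more posterior probabilities, would cost no patients.

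The arithmetic stands, and so does the observation that 25% has no stated source and is never set beside 38%. The step to a required change does not. The plan makes no inference about decitabine that needs restraining. That a single-arm trial cannot isolate one component holds at any benchmark. The extra probabilities come from the posterior already to be reported, and the comparison giving 0.58 needs an exchangeability that the documents do not establish. The hypothesis does name CR rates while the endpoint pools CR, CRp and CRi. However, section 9 defines CR separately, so tabulating it is routine reporting.

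**Conclusion.** No change to the plan follows. The missing link between 25% and 38% is a gap in explanation. As a futility floor for salvage treatment in general, 25% is consistent with the protocol's own background figures. The boundaries, sample size and estimator serve the stated objective of estimating the regimen's response rate.

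If the true rate were 38%, the cohort would complete about 77% of the time. That is proper behaviour for a rule meant to stop regimens at or below 25%, and completing accrual is not a claim of benefit over CIA. A careful analyst would read the planned interval (0.296 to 0.498 at 24/60) beside the CIA figure and conclude that the trial shows activity of the combination and cannot separate out decitabine.

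This rests on two readings: that the 25% describes salvage treatment broadly, which the plan does not say outright, and that the objective in section 1 governs the conclusions. Were the sponsor to claim an added effect of decitabine from this cohort, the objection would be to that claim, not to the design.

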5. TREATMENT PLAN

5.1. Study design

The study will include a phase I portion to determine MTD dose of clofarabine to be used in the subsequent phase II portion. Starting with Dose level 1, the patient will be enrolled by cohort of 3. Once the DLT assessment for the 3 patients is completed, a sequential of another cohort of 3 patients will be enrolled. If at any time, we see more than 30% patients experiencing DLT, we will de-escalate to dose level (-1). The same above monitoring rule will also be applied to dose level -1. A total of 18 patients will be enrolled. Once the phase II dose of clofarabine is established, additional patients will be enrolled in the phase II portion of the study.

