11. STATISTICAL CONSIDERATIONS

Phase I

First, phase I study is performed to assess the safety of different dosing schedules for clofarabine combined with fixed dosage of decitabine, idarubicin, and cytarabine. Two dose schedules are defined in table 1, and the starting dose schedule is dose level 1. A maximum of 18 AML patients will enroll in the phase I study.

Table 1: dose schedule

Dose level	Clofarabine 15 mg/m²/day IV daily
-1	Clofarabine daily for 3 days (days 6-8)
1	Clofarabine daily for 4 days (days 6-9)

Decitabine 20 mg/m² IV over approximately 1 hour daily for 5 days (days 1-5)

Idarubicin 10 mg/m² IV over approximately 30 minutes daily for 3 days (days 6-8)

Cytarabine 1 g/m² IV over approximately 2 hours daily for 5 days (days 6-10)

Dose Escalation Procedures

Starting with Dose level 1, the patient will be enrolled by cohort of 3. Once the DLT assessment for the 3 patients is completed, a sequential of another cohort of 3 patients will be enrolled. If at any time, we see more than 30% patients experiencing DLT, we will deescalate to dose level (-1). If no dose de-escalation occurs, with a total of 18 patients treated at dose level 1, dose level 1 will be considered as the MTD for the phase II part. If there is dose de-escalation, a cohort of 3 patients will be treated, Dose level -1 will be declared as MTD if there are ≤ 1 out of 6 patients experience DLT.

Phase II

Phase II part is a single arm study using the dosage schedule recommended from phase I. A maximum of 60 AML patients which includes 42 new patients and the 18 patients from phase I MTD level, and 20 ALL patients will be enrolled in the study. The trial will be continuously monitored regarding efficacy for each cohort, AML and ALL respectively. The toxicity will be jointly monitored for AML and ALL patients. The method of Thall, Simon, and Estey will be used to perform interim efficacy and safety monitoring.⁵³ The software Multc99.Version 2.1 was used to run the simulation.

Efficacy

The primary endpoint is the overall response which is defined as the best response (either CR, CRp, or CRi) within 56 days.

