11.2. ALL

For the ALL patients, the historical data suggested the overall response rate to current standard treatment is 20%. The target response rate would be 40% after the treatment. The trial will be continuously monitored. The study will be stopped early if the data suggest that:

$$\Pr(\pi > 0.2 | \text{data}) < 0.4$$

Here π is the overall response (OR) rate. That is, if at any time during the study we determine that there is a less than 40% chance that the average OR rate is greater than 20%, we will terminate the study. The OR rate is assumed to follow a non-informative prior of Beta (0.4, 1.6). The study will be stopped early if (The number of overall responses)/ (The number of patients evaluated) $\leq 1/8, 2/11, 3/17$.

Table 3: Operating characteristics for monitoring of overall response rate in ALL patients

True Response Rate	Early Stopping Probability	Median Sample size (interquartile)
0.15	0.85	8 (8,11)
0.2	0.7	11 (8, 20)
0.25	0.54	17 (8, 20)
0.3	0.38	20 (8,20)
0.35	0.26	20 (17, 20)
0.4	0.16	20 (20, 20)

Monitoring of non-hematological \geq grade 3 toxicities

With the concern of treatment related toxicity, the non-hematological toxicity (\geq grade 3) throughout all the cycles of treatment will also be closely monitored during the study for AML and ALL together.

Denote the probability of toxicity by P_E . We assume $P_E \sim \text{beta}(0.6, 1.4)$. Our stopping rule is given by the following probability statement: $\Pr(P_E > 0.3 \mid \text{data}) > 0.9$. That is, we will stop the trial if, at any time during the study, we determine that there is more than 90% chance that the toxicity rate is more than 30%. The study will be stopped early if (The number of non-hematological toxicities being grade 3 or higher)/ (The number of patients evaluated) $\geq 7/13, 8/15, 9/18, 10/21, 11/23, 12/26, 13/29, 14/32, 15/35, 16/38, 17/41, 18/43, 19/46, 20/49, 21/52, 22/55, 23/58, 24/61, 25/64, 26/67, 27/70, 28/73, 29/76, 30/79$. The operating characteristics are summarized in table 4.

Table 4: Operating characteristics for monitoring of non-hematological \geq grade 3 toxicities in AML or ALL patients

True Toxicity Rate	Early Stopping Probability	Median Sample size (interquartile)
0.25	0.15	80 (80, 80)
0.3	0.35	80 (27, 80)
0.35	0.63	42 (11, 80)
0.4	0.88	19 (7, 47)

Analysis method

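### The AML and ALL futility rules are each stated in two forms that disagree before patient 8; separately, the plan does not say that the AML looks at 8, 11 and 15 run during phase I.

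*Combined protocol and SAP*

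**What the plan says.** Section 11 (Phase II) announces that "The trial will be continuously monitored regarding efficacy for each cohort, AML and ALL respectively". Each cohort's rule is then given in two forms.

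- **AML (11.1).** With a Beta(0.5, 1.5) prior, the study terminates "if at any time during the study we determine that there is a less than 30% chance that the average OR rate" is above 25%. The next form is a list of responses over patients evaluated, beginning "1/8, 2/11, 3/15, 4/20, 5/24, 6/29, 7/33, 8/37" and ending at 13/59. Table 2 gives the operating characteristics for a maximum of 60.
- **ALL (11.2).** With a Beta(0.4, 1.6) prior, it terminates "if at any time during the study we determine that there is a less than 40% chance that the average OR rate" is above 20%. The list is 1/8, 2/11, 3/17. Table 3 gives the operating characteristics for a maximum of 20.

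Neither section sets a minimum number of patients before the rule applies.

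On the phases, section 11 states: "A maximum of 18 AML patients will enroll in the phase I study". It counts 60 AML patients in total, "which includes 42 new patients and the 18 patients from phase I MTD level". If there is no de-escalation, all 18 are treated at dose level 1. Section 5.1 adds: "Once the phase II dose of clofarabine is established, additional patients will be enrolled in the phase II portion of the study". The decision rules in 5.1 and in the phase I part of section 11 concern DLTs only. Section 2.6 confines ALL patients to phase II.

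**The concern.** A rule that terminates the study should lead to one action for any given data. Here someone who computes the posterior after a few patients and someone who reads the list can reach opposite decisions on the same counts. Tables 2 and 3 are the plan's only statement of how often each efficacy rule stops, and they describe only one of the two forms.

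The second matter concerns AML alone. New patients are added only once the phase II dose is fixed. Without de-escalation, AML patients 1 to 18 of the 60 are therefore the phase I patients, and the first three listed looks fall among them. The phase I text never mentions a response rule, so a team could run phase I on DLTs alone and lose the looks on which most of Table 2 depends.

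**Working it through.** **Inputs.** AML: threshold 0.25, prior Beta(0.5, 1.5), cut-off 0.30, N = 60 (11.1 and section 11). ALL: threshold 0.20, prior Beta(0.4, 1.6), cut-off 0.40, N = 20 (11.2 and section 11).

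**Formulas.** After s responses in n patients, Pr(π > p0 | data) = 1 − F(p0), where F is the Beta(a + s, b + n − s) distribution function. The rule stops when this falls below the cut-off. Stopping probabilities come from an exact binomial recursion: carry forward the distribution of s patient by patient, and remove the mass at or below the boundary at each look.

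**1. The plan's own figures, first look at 8.** For n ≥ 8 the probability criterion gives exactly the printed lists in both cohorts. Early stopping is then:

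| True rate | AML exact | Table 2 | ALL exact | Table 3 |
|---|---|---|---|---|
| 0.15 | – | – | 0.852 | 0.85 |
| 0.20 | 0.906 | 0.91 | 0.703 | 0.70 |
| 0.25 | 0.725 | 0.73 | 0.538 | 0.54 |
| 0.30 | 0.504 | 0.51 | 0.383 | 0.38 |
| 0.35 | 0.318 | 0.33 | 0.255 | 0.26 |
| 0.40 | 0.187 | 0.19 | 0.159 | 0.16 |

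Both tables reproduce. Two medians differ (AML at 0.25: 15 against 11; ALL at 0.20: 8 against 11). In those rows cumulative stopping sits at 0.4985 by patient 11 and 0.5033 at patient 8, so simulation error explains the difference.

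**2. The two forms before patient 8.** Posterior probability of exceeding the threshold:

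| Outcome | AML (stop if < 0.30) | ALL (stop if < 0.40) | Printed list |
|---|---|---|---|
| 0/1 | 0.253, stop | 0.245, stop | no entry |
| 1/5 | 0.348, continue | 0.424, continue | no entry |
| 1/6 | 0.275, stop | 0.353, stop | no entry |
| 1/7 | 0.217, stop | 0.293, stop | no entry |
| 1/8 | 0.170, stop | 0.242, stop | stop |

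With zero responses the posterior only falls as n grows, so 0/1 to 0/7 all meet the criterion. The forms therefore disagree at nine outcomes in each cohort: 0/1 to 0/7, 1/6 and 1/7.

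**3. The probability wording applied from patient 1.** At a true 40%, the first patient fails to respond with probability 0.60, which already meets the criterion. A response followed by five failures adds 0.4 × 0.6⁵ = 0.031 at patient 6. Later looks bring the totals to 0.649 (AML) and 0.641 (ALL).

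- AML at 0.20/0.25/0.30/0.35/0.40: 0.967/0.899/0.811/0.725/0.649.
- ALL at 0.15/0.20/0.25/0.30/0.35/0.40: 0.955/0.905/0.843/0.775/0.707/0.641.
- The median sample size is 1 in every row, against 8 to 60 in Table 2 and 8 to 20 in Table 3.

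**4. Share of AML stopping at looks 8, 11 and 15 (printed list).**

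- True 40%: the look at 8 stops with probability 0.6⁸ + 8 × 0.4 × 0.6⁷ = 0.0168 + 0.0896 = 0.1064. The three looks give 0.1064 + 0.0451 + 0.0195 = 0.171 of 0.187, or 91%.
- True 25%: 0.3671 + 0.1314 + 0.0693 = 0.568 of 0.725, or 78%.

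As an illustration only, if the first AML look were at patient 18 (boundary 3/18, then the list from 4/20), early stopping at 0.20/0.25/0.30/0.35/0.40 would be 0.87/0.64/0.37/0.18/0.07.

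**The case against.** The strongest reply on the first matter is that the list is the operational rule. It follows the probability statement directly, it has no entry below 8, and both tables reproduce from it. No sentence tells staff to compute a posterior instead. That is a good argument about intent, and I accept it. It does not remove the conflict, because the probability sentence is also written as a stopping instruction and says it applies at any time. Nor can a reader of section 11 assume that a list's first entry is the first look. The toxicity list starts at 7/13, yet Table 4 reports lower quartiles of 11 and 7 at true rates of 0.35 and 0.40. These are impossible unless trials could stop before patient 13. A first look at 5 or 6 returns them; a first look at 13 gives 19 and 14.

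A reader might infer that the trial really carries a 65% chance of abandoning a regimen at its target rate. The documents do not support that: the lists and tables point to a first look at 8, and the from-patient-1 reading is unlikely in practice. First looks at 6 or 7 are not in the plan either, so I rest nothing on them.

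On the second matter, a reader might infer that the phase I text contradicts the efficacy rule, or that Table 2 is wrong. Neither follows. Section 11.1 speaks of the whole study, the 18 phase I patients are counted in the 60, and Table 2's medians of 8 and 11 could not arise if monitoring began after patient 18. Everything stated points one way; what is missing is the statement itself. No passage sets a start at patient 18.

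**Conclusion.** The first matter holds as an inconsistency. Each futility rule has two forms that disagree at nine outcomes before patient 8 and agree from there on. Only the count form has the stated operating characteristics: at a true 40% it stops with probability 0.19 (AML) and 0.16 (ALL), against 0.65 and 0.64 for the literal probability wording. The lists are probably what was intended, so the defect is the missing minimum and not the lists or tables.

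The second matter is an unstated overlap, not a contradiction, and affects AML only. Table 2 holds only if the looks at 8, 11 and 15 are made during phase I, since they carry 0.171 of 0.187 at a true 40% and 0.568 of 0.725 at 25%. This is shown for the path without de-escalation only.

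The figures assume independent responses at a constant rate, fixed thresholds of 0.25 and 0.20, and every patient evaluated in order. The wording should be corrected; the design itself need not change.

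**What to change.** 1. In 11.1 and 11.2, state that the posterior-probability rule applies only once 8 patients in that cohort have been evaluated for response. The lists and Tables 2 and 3 then stand as printed.
2. In section 11, state that the AML efficacy rule runs on patients at the dose level currently being treated, including during phase I. It should be worded by current dose level because, without de-escalation, the MTD is declared only after 18 patients and is not known at looks 8, 11 and 15.
3. Have the sponsor reconcile how the efficacy count is handled if de-escalation occurs, including which patients then enter the 60. Table 2 has not been shown to hold on that path.

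Items 1 and 2 cost a few sentences, with no extra patients and no new simulation. Item 3 needs a decision by the sponsor and possibly a further set of operating characteristics for the de-escalation path.
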